90 assigned (1:1 allocation) to receive either the standard of care benzathine penicillin injection or 10-
91 days of oral cefixime. The study will require 2 years to be completed and each participant will be part
92 of the study for one year.

93

94 **Methods: Participants, interventions and outcomes**

95 **Study setting {9}**

96 The study will take place in 3 primary care HIV healthcare clinics and 1 wellness center of the
97 AIDS Healthcare Foundation in Los Angeles and Oakland, California. Healthcare clinics offer HIV
98 and sexually transmitted infection (STI) primary care services while wellness centers are walk-in
99 comprehensive sexual health clinics that offer HIV/STI screening services, STI treatment and other
100 prevention services.

101

102 **Eligibility criteria {10}**

103 The inclusion criteria are:

- 104 1) Clinically or laboratory confirmed new cases of early syphilis (primary, secondary, early
105 latent syphilis) with a plasma Rapid Plasma Reagin (RPR) $\geq 1:8$
- 106 2) 18 years of age or older, capable of providing informed consent
- 107 3) HIV infected individuals must have CD4 T cell count ≥ 350 cells/mm³ and be virologically
108 suppressed (viral load < 200 copies/mL) during the past 6 months
- 109 4) Able to travel to clinic once a day or be available for phone calls or receive text message for
110 at least 7-10 days

111 The exclusion criteria are:

- 112 1) Allergy to cefixime or penicillin
- 113 2) Pregnancy or a positive pregnancy test

- 114 3) Serofast RPR titer (prior titer $\geq 1:8$ without history of 4-fold titer decline)
- 115 4) Recent (within the past 7 days) or concomitant antimicrobial therapy with activity against
- 116 syphilis, namely azithromycin, doxycycline, ceftriaxone or other beta lactam antibiotics (e.g.
- 117 amoxicillin)
- 118 5) A medical condition or other factor that might affect their ability to follow the protocol

119

120 **Who will take informed consent? {26a}**

121 Patients must provide written, informed consent before any study procedures occur (randomization,

122 blood sample collection, treatment). Consent will be obtained by a study team member in a private

123 examination room.

124

125 **Additional consent provisions for collection and use of participant data and biological**

126 **specimens {26b}**

127 Patients will also sign a Health Insurance Portability and Accountability Act (HIPAA) release form

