128 allowing access to clinical and laboratory data, including their HIV test results.

129

130 **Interventions**

131 **Explanation for the choice of comparators {6b}**

132 This is a pilot, non-comparative clinical trial designed to collect preliminary efficacy data. It

133 includes an “experimental arm” of participants receiving cefixime and a contemporaneous “control

134 arm” of participants receiving benzathine penicillin. The study was not designed to be adequately

135 powered to show a statistically significant difference in the efficacy between the penicillin and

136 cefixime arms.

137

138 **Intervention description {11a}**

139 Eligible participants who provide their consent are randomized to the two arms of the study.
140 Initially, the study team collects demographic (age, gender, race, ethnicity, contact, sexual
141 orientation) and clinical information (most recent RPR titer, CD4 T cell count, HIV viral load). A
142 venipuncture blood sample is collected by trained clinic staff and it is sent to the laboratory for
143 testing. Testing is conducted on serum using the Arlington scientific RPR test kit (Arlington,
144 Virginia) (22). Participants are randomly assigned to the two treatment groups. Participants
145 assigned to the penicillin arm will receive 1 dose of 2.4M IU benzathine penicillin G on the day of
146 enrollment. Participants who are assigned to the cefixime arm will be given 20 capsules of oral
147 cefixime 400mg on the day of enrollment to take for the following 10 days. Study staff observed
148 receipt of the first dose. Subjects in the cefixime arm will then be asked to return for a clinical
149 assessment or have a phone call assessment with the study team member 2 weeks following
150 enrolment.

151 Study staff will follow up with all participants at 3, 6, and 12 months. In each follow up,
152 participants are asked questions regarding symptoms, antibiotic use in the past 3 months and
153 number of sex partners with whom they had condom-less sex in the past 3 months. A new
154 venipuncture blood sample is also collected for RPR testing

155
156 **Criteria for discontinuing or modifying allocated interventions {11b}**

157 Participants may request to leave the study or they may be withdrawn due to study-related adverse
158 events. If a subject is discontinued from study participation due to an adverse event, they will be

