159 evaluated by the study clinicians for the need of additional treatment for syphilis. Safety data will
160 be collected on any subject who is withdrawn from the study.

161 Participants in both study groups may receive additional treatment with penicillin, if they show no
162 response to treatment (stable or absence of 4-fold decline at 6 months).

163

164 **Strategies to improve adherence to interventions {11c}**

165 To ensure retention of participants, follow-up visits will be scheduled to coincide with routine clinic
166 appointments for HIV care or preventive sexual health appointments, which occur every three
167 months. In addition, study staff will contact participants, either over the phone or via text message,
168 before their scheduled follow-up appointment. Finally, participants will receive reimbursement for
169 their time and transportation in the form of a gift card.

170

171 **Relevant concomitant care permitted or prohibited during the trial {11d}**

172 Usual HIV care and treatment for the participant will continue throughout the trial. Concomitant
173 antibiotic use during the participation in the study duration of the trial will be recorded.

174

175 **Provisions for post-trial care {30}**

176 Once participants complete the study, they will be able to continue receiving clinical care from the
177 clinics. Participants study records will be reviewed and if necessary, additional treatment for
178 syphilis will be administered according to the standard of care protocol.

179

180 **Outcomes {12}**

181 The primary outcome is the successful treatment of early syphilis by the 3-, or 6-month follow-up.
182 The participants' RPR titer will be used as the primary measure of outcome. Successful treatment is
183 defined as an equal or greater than 4-fold RPR titer decrease, from baseline to 3 or 6 months after
184 treatment.

[figure not shown]
185

186 **Participant timeline {13}**

187 Participants will be part of the study for 12 months. Study evaluations will occur at 3, 6- and 12-
188 months post-treatment. See Figure 1 for the participant timeline for the trial.

189

190 **Figure 1: Participant Enrollment and Follow-Up Schedule**

191

192

193 **Sample size {14}**

194 The primary analysis will compute the proportion of subjects with a 4-fold decrease (from study
195 entry RPR) in RPR titer from baseline at 6 months in the per protocol analysis population. If we

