196 assume a sample size of 40 and the proportion of subjects with a 4-fold decrease in RPR from
197 baseline at 6 months to be 0.9 (90%), we would have a 95% confidence interval of (0.76, 0.97). To
198 calculate the number of subjects required to enroll to reach 40 evaluable subjects in the PP analysis
199 population, the assumptions that 20% of subjects will be excluded from the PP analysis population
200 (due to loss to follow-up or non-compliance with study medication schedule). Under that
201 assumption, enrolling 50 subjects will provide 40 subjects in the PP analysis population.

202

203 **Recruitment {15}**

204 Participant recruitment will occur in 4 AIDS Healthcare Foundation (AHF) Clinics based in Los
205 Angeles, California and Oakland, California. Study clinicians will review the medical and
206 laboratory records of syphilis cases returning for treatment before the scheduled clinical visit and if
207 the participant fulfils the eligibility criteria, they will be invited to participate in the study.

208

209 **Assignment of interventions: randomization**

210 **Sequence generation {16a}**

211 After consent, participants are randomly assigned to the study arms with a 1:1 allocation. We will
212 use a simple randomization method with a shuffled deck of sealed envelopes that contain a card
213 with the assigned treatment. The cards are created before the enrollment period and distributed to
214 each of the study sites. No other factors will be taken into consideration for randomization.

215 **Concealment mechanism {16b}**

216 The envelopes containing the randomization cards are sealed, thus the team member conducting
217 enrollment does not know the content of the envelope.

218 **Implementation {16c}**

219 The study staff will ask the participant to select a sealed envelope from the shuffled deck. After
220 selecting the envelope, the participant will reveal the treatment to themselves and the study staff.

221

222 **Assignment of interventions: Blinding**

223 **Who will be blinded {17a}**

224 This is an open label clinical trial, while neither the participants nor the study staff will be blinded
225 to the assigned treatment, staff performing statistical analyses will be masked to treatment
226 assignment.

227 **Procedure for unblinding if needed {17b}**

228 Not applicable.

229 **Data collection and management**

230 **Plans for assessment and collection of outcomes {18a}**

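### A 4-fold RPR fall first seen after another syphilis-active antibiotic counts as study-treatment success, because the scoring rule places no condition on such drugs

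*Combined protocol and SAP*

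**What the plan says.** Four parts of the combined protocol and SAP bear on this.

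- **Outcomes {12}.** Success is "defined as an equal or greater than 4-fold RPR titer decrease, from baseline to 3 or 6 months after" treatment. The test is on titre alone.
- **Statistical methods {20a}.** The PP set requires that the patient meets the eligibility criteria, completed treatment, reported no adverse event, came back at month 3 and/or month 6, and has an evaluable RPR. *Evaluable* is not defined, and antibiotics taken in follow-up are not mentioned. Each arm's proportion is reported separately with an exact 95% interval.
- **Eligibility {10}, exclusion criterion 4.** This excludes patients with "Recent (within the past 7 days) or concomitant antimicrobial therapy with activity against" syphilis, and names azithromycin, doxycycline, ceftriaxone and other beta-lactams.
- **Concomitant care {11d} and intervention description {11a}.** During the trial, "antibiotic use during the participation in the study duration of the trial will be recorded". At each follow-up visit "participants are asked questions regarding symptoms, antibiotic use in the past 3 months and" partners.

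The plan therefore collects the information but does not say how the analysis uses it.

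**The concern.** The protocol itself classes the criterion 4 drugs as active against syphilis. Suppose a patient has no 4-fold fall at month 3, is given one of these drugs for another infection, and shows a 4-fold fall at month 6. Under {12} and {20a} that patient is a success of the assigned arm, although another active drug may have produced the fall.

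The error runs in one direction. Extra active treatment can turn a non-response into a response, so crediting the later fall either overstates the arm's success or makes no difference. Because each arm is reported on its own, a similar error in both arms does not cancel as it might in a difference. The proportion on cefixime is the trial's main product ("This is a pilot, non-comparative clinical trial designed to collect preliminary efficacy data"), so what it credits to cefixime should be stated.

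Exposure is plausible. Under Study setting {9}, the clinics offer HIV "and sexually transmitted infection (STI) primary care services while wellness centers are walk-in" "comprehensive sexual health clinics that offer HIV/STI screening services, STI treatment and other" prevention services. This describes the services at the sites and says nothing about how often trial patients receive these drugs.

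**Working it through.** **Inputs.** From Sample size {14}: 40 evaluable PP patients, success 0.9, interval (0.76, 0.97), 20% excluded, 50 enrolled. From {20a}: exact binomial interval. Assumed, because the documents do not give them: k, the number of patients in an arm whose only 4-fold fall came after another active antibiotic; q, the share of those k who would have responded in time without it; and whether 40 is one arm or both.

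**Step 1: reproduce the plan's figures.** The plan says to "assume a sample size of 40 and the proportion of subjects with a 4-fold decrease in RPR from" baseline of 0.9, so 0.9 × 40 = 36 successes. The exact (Clopper-Pearson) limits are the 2.5% point of Beta(36, 5) = 0.763 and the 97.5% point of Beta(37, 4) = 0.972, which match (0.76, 0.97). Enrollment is 40/(1 − 0.20) = 50, which also matches.

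**Step 2: find where the scoring matters.**

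| Patient exposed to another active antibiotic | As written | If later falls are not credited |
|---|---|---|
| 4-fold fall documented before the antibiotic | success | success |
| 4-fold fall first documented after it | success | non-success |
| No 4-fold fall by month 6 | non-success | non-success |

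Only the middle row changes.

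**Step 3: size.** The overstatement is k × (1 − q)/n. With q = 0 it is at its upper bound.

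- n = 40 (40 taken as one arm): k = 1 gives 35/40 = 87.5% (0.732 to 0.958); k = 2 gives 34/40 = 85.0% (0.702 to 0.943); k = 3 gives 33/40 = 82.5% (0.672 to 0.927). The upper bounds are 2.5, 5.0 and 7.5 points. With q = 0.5 they halve to 1.25, 2.5 and 3.75 points.
- n = 20 (40 taken as both arms; 40/2 under 1:1 allocation): the base is 18/20 = 90% (0.683 to 0.988). k = 1 gives 17/20 = 85%; k = 2 gives 16/20 = 80% (0.563 to 0.943). Each patient counts for up to 5 points.

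**Step 4: compare with sampling error.** The interval width is 0.972 − 0.763 = 0.209, about 21 points, for n = 40, and 0.988 − 0.683 = 0.305, about 30 points, for n = 20. One or a few patients move the estimate by much less than that.

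**Step 5: what exclusion would do instead.** From 36/40, dropping one exposed late success gives 35/39 = 89.7%. Dropping one exposed failure gives 36/39 = 92.3% (0.791 to 0.984). Exclusion can therefore raise the proportion by removing patients who failed despite extra active treatment. This is why the main rule should keep exposed patients in PP.

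**The case against.** **The plan already has a rule.** On the natural reading, PP patients are scored on titre. This is correct, and the point is about what that rule credits. A reader might go further and infer that criterion 4 runs through follow-up, because {11d} also uses the word *concomitant*, so that the plan carries two competing PP definitions. The documents do not support that. Criterion 4 is an eligibility item, Recruitment {15} has eligibility checked from records before the visit at which patients are invited, and {14} attributes PP exclusions only to lost follow-up or not keeping to the medication schedule. {11d} also adds that it means the period of participation, which criterion 4 does not. What does remain open is the undefined *evaluable* RPR, which an analyst could use to set aside a post-antibiotic result.

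**Some of these patients would have responded anyway.** This stands. The figures in Step 3 are upper bounds, and refusing credit will understate the effect for some patients.

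**The trial is a pilot with no success threshold, and its analysts are masked ({17a}).** The first part limits the consequence to how a proportion is read. Masking limits arm-specific choices but does not change what is credited.

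**Penicillin given for non-response.** A reader might infer that this contaminates the primary outcome. {11b} ties it to the lack of a 4-fold decline at 6 months, so on that wording it follows the scored RPR and is not part of this point.

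**Antibiotic use is recorded anyway.** {11d} and the release giving access to clinical data ({26b}) do support data capture. The gap is in the visit question: it looks back 3 months, while PP admits patients seen only at month 6, so months 0 to 3 may go unasked.

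**Conclusion.** The concern holds as a minor point. As written, the scoring can credit the study treatment with a response first seen after another drug that the protocol itself lists as active against syphilis. The error can only favor the arm concerned.

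Its size rests on three assumptions: the number of such patients, the share who would have responded anyway, and whether 40 is one arm or both. Per patient it is at most 2.5 points with 40 in the arm, or 5 points with about 20. Because exposure frequency is not given, the documents do not support a claim that the reported proportion will be materially wrong, or that such exposure is common at these sites. The interval will be far wider than the likely shift, but it covers sampling error and not misattributed response.

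**What to change.** Add to {20a}, for both arms:

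> A 4-fold fall first documented after a syphilis-active antibiotic (criterion 4 list or penicillin) other than the assigned study treatment, started after enrollment and before that RPR, is not credited as success. A 4-fold fall documented before the antibiotic counts as success. Exposed patients without a 4-fold fall remain in PP as non-successes.

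The words *other than the assigned study treatment* are needed because both study drugs are beta-lactams. Without them the rule would catch every post-treatment RPR.

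Report two sensitivity analyses: (a) all patients scored on titre, as the plan now reads; (b) exposed patients without an earlier 4-fold fall excluded. Give the number of exposed patients per arm.

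Change the look-back of the visit question on antibiotics from 3 months to the time since enrollment or the last study visit, or take the information from the clinic record. Check that the form captures the drug name and an approximate date.

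The cost is one paragraph of analysis text and a small change to a form. The main figure may be slightly lower and is conservative, since some exposed patients would have responded by month 6 anyway; analysis (a) shows by how much. The change governs scoring only, not which antibiotics patients may receive.

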231 A venipuncture blood sample will be collected at 3, 6, and 12 month visits and it will be tested for
232 RPR titer.. Study data collected on baseline include basic demographic information, sexual history,
233 laboratory tests (CD4 count, viral load, RPR titer). On each follow up visit, sexual history,
234 antibiotic use, symptoms and the RPR titer will be collected. Data will be collected on paper data
235 collection forms and will be entered into Research Electronic Data Capture (REDCap) (23, 24).

236 **Plans to promote participant retention and complete follow-up {18b}**

237 Study follow-up visits are scheduled to coincide with routine clinic appointments within AHF.
238 Study staff will send participants a 1 month, 2 week, and 1 day notification prior to their follow-up
239 appointment.

240 **Data management {19}**

241 Participant data will be collected on paper data collection forms and entered into RedCap. Data that
242 will be entered into RedCap include participant information (name, date of birth, medical record
243 number, contact information) and laboratory results.

244 **Confidentiality {27}**

245 Redcap servers are encrypted, HIPAA-compliant, password protected and accessible only by
246 designated study members. Hard copy data collection forms will be stored into a locked cabinet
247 with limited access only to designated members.

248

249 **Plans for collection, laboratory evaluation and storage of biological specimens for genetic or** 250 **molecular analysis in this trial/future use {33}**

251 There are no plans in this trial to evaluate or store biological specimen for genetic or molecular
252 analysis for future use.

253

254 **Statistical methods**

255 **Statistical methods for primary and secondary outcomes {20a}**

256 The primary analysis for the main outcome will be conducted on the “Per Protocol” (PP)
257 population. This will include participants who satisfy the inclusion and exclusion criteria,
258 completed treatment (i.e. received the penicillin injection or received all of the cefixime pills),
259 report no adverse events, returned for follow-up visits (3 and/or 6 months) and have an evaluable
260 RPR result.

261 For each treatment group, we will calculate the proportion of PP participants who achieved a 4-fold
262 RPR titer decrease at 3, or 6-months post-treatment and the exact binomial 95% confidence
263 interval.

264

265 **Interim analyses {21b}**

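### The 20% allowance in Sample size {14} leaves out the adverse-event exclusion in {20a}, so 50 enrolled gives 40 per-protocol participants only if that exclusion is negligible or already counted

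*Combined protocol and SAP*

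**What the plan says.** Sample size {14} sets a target of 40 evaluable participants and a response proportion of 0.90, with a 95% interval of 0.76 to 0.97. It describes the allowance as "population, the assumptions that 20% of subjects will be excluded from the PP analysis population" and gives the reasons in parentheses: "due to loss to follow-up or non-compliance with study medication schedule". It concludes that "enrolling 50 subjects will provide 40 subjects in the PP analysis population".

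Statistical methods {20a} makes the PP population the primary analysis set. Membership requires five things: meeting the eligibility criteria, completing treatment, a return visit at 3 and/or 6 months, an evaluable RPR, and that participants "report no adverse events". The last condition carries no grade, no relatedness to study drug and no time window. The analysis is a proportion with an exact binomial interval for each treatment group.

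No section gives an expected adverse-event rate. The Background {6a} says only that the cefixime profile is favourable.

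**The concern.** The planning section and the analysis section describe the same population by different rules. Completing treatment and returning for follow-up match the two reasons listed in {14}. The adverse-event condition has no counterpart there. Read literally, one minor event removes a participant who was treated, came back and has a usable titre.

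Such reports are likely to come to light. The Intervention description {11a} has staff ask about symptoms at every follow-up visit, and the cefixime arm has an extra contact at 2 weeks.

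Two things are at stake. The first is the basis for the protocol's only sample-size statement and its only precision figure. The second is that the condition drops evaluable participants from the primary efficacy analysis because of something that happened after treatment. That is a selection effect whose direction the documents do not allow one to predict.

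**Working it through.** **Inputs.** From {14}: PP target 40, response 0.90, PP exclusion 20%, enrolment 50. From {20a}: exact binomial 95% interval, and the adverse-event condition. Assumed: a, the proportion reporting an adverse event among participants who are otherwise evaluable. The documents give no value, so a range is shown.

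**1. Reproducing the plan.**
- Enrolment: 40 / (1 − 0.20) = 50. This matches.
- Interval: 0.90 × 40 = 36; the exact (Clopper-Pearson) interval for 36/40 is 0.763 to 0.972. This matches the stated 0.76 to 0.97.

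**2. Adding the adverse-event condition.** If the two named reasons use up the whole 20%:

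expected PP = 50 × 0.80 × (1 − a)

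| Assumed a | Expected PP from 50 | Exact 95% interval at 0.90 | Fall in lower limit from 0.763 |
|---|---|---|---|
| 0% | 40 | 0.763 to 0.972 | none |
| 5% | 38 | 0.759 to 0.973 | 0.004 |
| 10% | 36 | 0.754 to 0.975 | 0.009 |
| 20% | 32 | 0.742 to 0.977 | 0.021 |
| 30% | 28 | 0.727 to 0.980 | 0.036 |

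Below n = 40, 0.90 × n is not a whole number (for example 0.90 × 36 = 32.4). Those limits come from the beta-quantile formula at the non-integer count and are approximate.

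**3. The same question in reverse.** For 40 of 50 to hold with adverse events counted, loss and non-compliance together (L) must satisfy (1 − L)(1 − a) ≥ 0.80, so L ≤ 1 − 0.80/(1 − a).
- a = 5%: L ≤ 15.8%
- a = 10%: L ≤ 11.1%
- a = 20%: L ≤ 0%

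The 40 can therefore survive a modest adverse-event rate, but only if loss and non-compliance run below 20%. The protocol makes no such assumption.

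**4. Other unnamed reasons.** {20a} also requires eligibility and an evaluable RPR, and {14} names neither. Removing the adverse-event condition alone therefore does not make the two lists identical.

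**The case against.** A reader might infer that 50 enrolled cannot give 40. The documents do not support that, for three reasons.

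- The 20% is worded as the total PP exclusion, with reasons attached. An incomplete list of reasons does not show that the total is wrong, and step 3 shows combinations in which 40 is still reached.
- Some participants with adverse events may already be counted. Under {11b} they may be withdrawn for study-related events, and some of these would appear as lost or non-compliant. Defining a among the otherwise evaluable avoids double counting, but a could then be small.
- No rate is given. At about 5% or less the expected shortfall is two participants at most.

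The effect on precision is also modest. Even at 20%, the lower limit at 0.90 moves by about 0.02, in a non-comparative pilot with no success threshold. A more alarming picture comes from looking at each arm: 18/20 gives 0.683 to 0.988 with no adverse-event loss at all. That width comes from splitting 40 between two arms, if 50 is the total, which {14} does not say explicitly. It is a separate matter and should not be charged to this exclusion.

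All of this stands, and it limits the size of the point. It does not remove the mismatch. {14} and {20a} still define the PP set differently, and no other section reconciles them.

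**Conclusion.** There is no arithmetic error. The point is an inconsistency between the stated basis for the sample size and the PP definition used in the primary analysis. Fifty enrolled gives 40 PP participants only if adverse-event exclusions are negligible or already within the 20%, and the protocol says neither.

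The shortfall runs from 2 participants at an assumed 5% adverse-event proportion to 12 at 30%. This rests on two assumptions: that loss and non-compliance use the full 20%, and the chosen value of a. If either is too pessimistic, the shortfall shrinks or disappears.

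The loss of precision alone would make this a minor note. The stronger reason to act is that the same condition removes participants with usable outcome data from the primary efficacy analysis, and correcting it costs very little.

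**What to change.** 1. Delete the adverse-event condition from the PP definition in {20a}. Treated, followed participants with an evaluable RPR then stay in the efficacy analysis, and adverse events are reported separately as safety data.
2. If the condition is kept, restate in {14} the expected PP number for 50 enrolled and the matching exact interval, with an explicit adverse-event assumption. For example, at 10% these are 36 participants and about 0.754 to 0.975 at 0.90.
3. In either case, say in {14} that the 20% covers all the exclusion reasons in {20a}, including eligibility and evaluable RPR.

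The first option costs a one-clause amendment to the PP definition. The second costs a sentence in {14} and a less favourable planning figure. Neither asks for more enrolment. Recruitment is under way according to Trial status, so the change should be dated and made before the primary analysis.

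### The planned precision, 95% CI (0.76, 0.97), counts all 40 per-protocol patients, but the analysis is by arm with about 20 each, which gives about (0.68, 0.99).

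*Combined protocol and SAP*

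**What the plan says.** Section {14}, Sample size, describes a single proportion in the PP population. Its inputs are to "assume a sample size of 40 and the proportion of subjects with a 4-fold decrease in RPR from" "baseline at 6 months to be 0.9 (90%), we would have a 95% confidence interval of (0.76, 0.97"). Enrolment is then inflated for exclusions ("population, the assumptions that 20% of subjects will be excluded from the PP analysis population"), with the result that "assumption, enrolling 50 subjects will provide 40 subjects in the PP analysis population". The section does not mention arms.

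Three other statements determine what that 40 means:

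- Section {8}, Trial design: participants are "assigned (1:1 allocation) to receive either the standard of care benzathine penicillin injection or 10" days of oral cefixime. Section {16a} repeats the 1:1 ratio and calls the method simple randomization.
- Section {20a}, Statistical methods: the PP population is made up of those who, among other conditions, "completed treatment (i.e. received the penicillin injection or received all of the cefixime pills"). It therefore covers both arms.
- Section {20a} again: "For each treatment group, we will calculate the proportion of PP participants who achieved a 4-fold" fall in titer, with an exact binomial 95% interval.

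**The concern.** The sample size section puts all 40 PP patients into one proportion, whereas the primary analysis divides those patients between two arms and estimates each arm separately. Section {20a} plans no pooled proportion. A pooled figure would also mix penicillin and cefixime responses and would not address the objective in section {7}, which is the efficacy of cefixime. The stated interval therefore belongs to no estimate that the analysis section plans.

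This matters because the width of that interval is the only operating characteristic the plan gives. Section {6b} disclaims power for a comparison between arms, so the interval around the cefixime proportion is the trial's main inferential result. Anyone judging whether the study is large enough to be informative is shown a precision that the cefixime arm will not have.

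**Working it through.** **Inputs.** Evaluable sample 40, success 0.90, PP exclusion 20% and enrolment 50 (section {14}); 1:1 allocation (sections {8} and {16a}); exact binomial interval for each treatment group (section {20a}).

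**Formula.** For x successes in n, the exact (Clopper-Pearson) 95% limits are:

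- lower = 2.5% quantile of Beta(x, n − x + 1)
- upper = 97.5% quantile of Beta(x + 1, n − x)

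**Step 1: reproduce the plan's figures.** 0.90 x 40 = 36. For 36/40 the limits are the 2.5% quantile of Beta(36, 5) = 0.7634 and the 97.5% quantile of Beta(37, 4) = 0.9721. This matches (0.76, 0.97). Other methods do not match: Wilson gives (0.769, 0.960) and Wald (0.807, 0.993). Enrolment is 40 / (1 − 0.20) = 50, which also matches. The stated interval therefore uses all 40 patients in one estimate, and the inflation contains no factor of two for the arms.

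**Step 2: number per arm.** 50 / 2 = 25 randomised per arm, and 25 x 0.80 = 20 evaluable per arm.

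**Step 3: interval per arm.** 0.90 x 20 = 18. For 18/20 the limits are the 2.5% quantile of Beta(18, 3) = 0.6830 and the 97.5% quantile of Beta(19, 2) = 0.9877.

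| | n | Successes | Exact 95% CI | Width |
|---|---|---|---|---|
| As stated | 40 | 36 | (0.763, 0.972) | 0.209 |
| Per arm as designed | 20 | 18 | (0.683, 0.988) | 0.305 |

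The width ratio is 0.3046 / 0.2087 = 1.46. The lower limit falls by 0.763 − 0.683 = 0.080.

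**Step 4: how far the count of 20 could move.** If each assignment is an independent 50:50 draw and 20% are excluded in each arm, the cefixime PP count is Binomial(50, 0.4), with a 95% range of 13 to 27. If the envelopes form a balanced deck that is used up, so that each arm has exactly 25, the count is Binomial(25, 0.8), with a 95% range of 16 to 24. Both are centred on 20. Intervals near that count are (0.669, 0.987) for 17/19 and (0.696, 0.988) for 19/21. If the cefixime arm lost more patients, 14/16 would give about (0.62, 0.98).

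**Step 5: what the stated interval would require.** Forty evaluable in each arm is 80 in total, and 80 / 0.80 = 100 enrolled.

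**The case against.** The strongest reply is that section {14} labels neither 40 nor 50 as a total or a per-arm figure. A single-proportion calculation written for one group, with the words 'per arm' left out, is coherent: 40 evaluable and 50 enrolled in each arm, 100 in all. The stated interval would then be correct. This possibility cannot be excluded, but nothing in the document supports it. No section gives a per-arm figure or a total of 100, and the population to which the 40 are assigned is defined across both arms. On that reading the text would still need correcting, because the enrolment target would be 100 and the protocol never says so.

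Other points can be granted without changing the result:

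- The arithmetic is right for n = 40. The fault lies in the number to which it is applied.
- The trial is a non-comparative pilot with no success threshold or decision rule tied to 0.76 or 0.70. The final report would give an exact interval on the actual number per arm, so the analysis itself is not biased. What is wrong is the planning statement. The pilot label answers a complaint about power between arms, not one about precision within an arm.
- The 13 to 27 range depends on independent assignment. The shuffled deck in section {16a} may be balanced, which would narrow the range to 16 to 24 but leave its centre at 20.

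**Conclusion.** The concern holds. As written, the design gives about 20 evaluable patients per arm, and at 90% success the exact 95% interval in each arm is (0.68, 0.99), not (0.76, 0.97). The interval is 46% wider, and its lower limit is 8 points lower and below 70%. The sample size section claims a precision that the trial's own primary analysis will not deliver, so the statement is wrong rather than merely incomplete.

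The conclusion rests on two assumptions. The first is that 50 is total enrolment, which is how the text reads. The second is that the 20% exclusion applies equally to both arms. The documents give no exclusion rate by arm. Twenty may be optimistic for cefixime, where per-protocol completion means all 20 capsules over 10 days, against a single injection in the penicillin arm.

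**What to change.** Restate section {14} by arm so that it matches section {20a}. Suggested wording:

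> Fifty participants in total will be randomised, about 25 to each arm. Allowing for 20% exclusion from the PP population in each arm, about 20 per arm are expected to be evaluable. If 18 of 20 (90%) respond, the exact 95% confidence interval for that arm is (0.68, 0.99).

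If 50 per arm was intended, keep (0.76, 0.97), label both 40 and 50 as per arm, and state the total enrolment of 100.

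On the plain reading, the cost is a wording amendment and a less favourable stated precision. No extra enrolment and no change to the analysis are needed. Enrolling 100 would be required only if the sponsor wants to retain the stated precision in each arm.
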